## 1. OBJECTIVE, SPECIFIC AIMS, BACKGROUND, AND SIGNIFICANCE

### 1.1 OBJECTIVE

The main objective of this study is to investigate the effect of inhaled nitrite delivered in a dose escalation manner in patients on background pulmonary hypertension therapy (ETRA, PDE5I, or prostacyclin analog) on cardiopulmonary hemodynamics in subjects with pulmonary hypertension.

### 1.2 SPECIFIC AIMS

#### Hypothesis:

- We hypothesize that inhaled nitrite treatment will reduce pulmonary vascular resistance. Our primary endpoint will be the change in pulmonary vascular resistance (PVR) measured by right heart catheterization.
- We hypothesize that inhaled nitrite treatment will improve cellular and global right ventricular signaling and function.
- We hypothesize that nitrite will be safe and well-tolerated in patients on background PAH therapy (PDE-5I and ETRA)

#### Specific Aims:

- 1) To determine the efficacy of inhaled nitrite, on the change in pulmonary vascular resistance measured by right heart catheterization.
- 2) To explore the effect of inhaled nitrite on echocardiographic and hemodynamic parameters measured: SVR, RV systolic (dP/dtmax/IP, PWRmax/EDV, RV EF, TAPSE), RV diastolic function (dP/dtmin, Tau), Pulmonary vascular impedance / Wave Intensity
- 3) To evaluate the safety of inhaled nitrite on systemic blood pressure in patients on background therapy for PAH.
- 4) To identify the pharmacokinetic relationships of nitrite measures of drug exposure and plasma cGMP, using blood sampling.
- 5) To identify the changes in mitochondrial oxygen consumption, using analysis of platelets

- 6) To compare effects of inhaled nitrite on pulmonary vascular resistance with inhaled NO gas at 40 ppm.

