## PROTOCOL SYNOPSIS

Protocol Title:	A Dose Escalation Study to Evaluate the Effect of Inhaled Nitrite on Cardiopulmonary Hemodynamics in Subjects with Pulmonary Hypertension	
Protocol Number:	PRO 11080686	
NCT Number:	NCT01431313	
Version # and Date:	Version 3.0/October 12, 2017	
Clinical Phase:	Phase II clinical investigation	
Investigational Drug:	Sodium Nitrite Inhalation Solution (AIR001 Inhalation Solution)	
Trial Site:	Single-Center Trial	
Sponsor:	[name] Associate Professor of Medicine University of Pittsburgh Heart and Vascular Institute	
Investigator:	[name], MS, FACC Associate Professor of Medicine University of Pittsburgh UPMC Heart and Vascular Institute	
Sub-Investigators:	[name] [name]	[name] [name] [name]
Study Monitor:	[name] Associate Professor of Medicine University of Pittsburgh Heart and Vascular Institute	
Research Facilities:	University of Pittsburgh Medical Center [name]	

Clinical Laboratories:	University of Pittsburgh Medical Center [name]
Manufacturer:	Aires Pharmaceuticals, Inc.
Study Rationale:	
Inhaled nitric oxide has been demonstrated to improve pulmonary hemodynamics in subjects with pulmonary arterial hypertension (PAH).
 
We hypothesize that inhaled nitrite provides a therapeutic approach for patients with PAH for the following reasons:
 

1. Inhaled nitrite therapy provides a potent, effective treatment that will vasodilate the pulmonary circulation (reduce pulmonary vascular resistance), reduce mean pulmonary artery pressure, and increase cardiac output.

2. This study will provide valuable efficacy and safety insights into the interactions between NO and nitrite, both direct NO generators, with or without background PH therapy, particularly phosphodiesterase type-5 inhibitors (PDE-5I), on pulmonary hemodynamics and right heart function.

3. This study will also provide novel assessments of right ventricular global myocardial function.

4. The results obtained from this study will also lay the groundwork for future large-scale clinical trials that are needed to investigate the efficacy of inhaled nitrite and/or its long-term effects on pulmonary hemodynamics in patients with pulmonary hypertension.

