Study Objectives:	The main objective of this study is to investigate the effect of inhaled nitrite delivered in a dose escalation manner in patients that may be on background pulmonary hypertension therapy; endothelin receptor antagonist (ETRA), PDE-5I, or prostacyclin analog on cardiopulmonary hemodynamics in subjects with pulmonary hypertension.
Study Hypothesis:	

• We hypothesize that inhaled nitrite treatment will improve clinical parameters of pulmonary vascular and right heart function. Our primary endpoint will be the change in pulmonary vascular resistance (PVR) measured by right heart catheterization.

• We hypothesize that inhaled nitrite treatment will improve global right ventricular function.

	
 
• We hypothesize that inhaled nitrite may be delivered safely, based on stable mean arterial blood pressure with minimal dose limiting symptoms, in patients on background PAH therapy, particularly PDE-5I (sildenafil, tadalafil).
 

Study Aims:
	
Specific Aims:
 
 
1. To determine the efficacy of inhaled nitrite, on the change in pulmonary vascular resistance measured by right heart catheterization.
 
2. To explore the effect of inhaled nitrite on echocardiographic and hemodynamic parameters measured: SVR, RV systolic (dP/dtmax/IP, PWRmax/EDV, RV EF, TAPSE), RV diastolic function (dP/dtmin, Tau), Pulmonary vascular impedance / Wave Intensity.
 
3. To evaluate the safety of inhaled nitrite on systemic blood pressure in patients on background therapy for PAH.
 
4. To identify the pharmacokinetic relationships of nitrite measures of drug exposure and plasma cGMP, using blood sampling.
 
5. To identify the changes in mitochondrial oxygen consumption, using analysis of platelets.
 
6. To compare effects of inhaled nitrite on pulmonary vascular resistance with inhaled NO gas at 40 ppm.
 

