Inclusion Criteria:	
WHO Group I PAH (n = 20)          Diagnosis of RHC confirmed WHO Group I PAH in any of the following 3 categories:
 
 
• Idiopathic, primary or familial pulmonary arterial hypertension (IPAH, PPH, or FPAH)
 
 
OR
 
 
• PAH associated with one of the following connective tissue diseases (CTD):             
 
i. Systemic sclerosis (scleroderma)
 
ii. Limited scleroderma
 
iii. Mixed connective tissue disease
 
iv. Systemic lupus erythematosus
 
v. Overlap syndrome;
 
 
 
 
OR
 
 
• PAH associated with:             
 
i. Human immunodeficiency virus (HIV) infection;
 
ii. Simple, congenital systemic-to-pulmonary shunts at least one year post-surgical repair.
 
iii. Exposure to legal drugs, chemicals and toxins, such as fenfluramine, derivatives, other anorexigens, toxic rapeseed oil or L-tryptophan. Subjects with PAH associated with illegal drug use, such as methamphetamine, are excluded.
 
 
 
 
Stable PH for at least 3 months if on disease specific therapy.
 
WHO Group II PH (=20)  Diagnosis of RHC confirmed WHO Group II PH by:
 
 
• Pulmonary capillary wedge pressure (PWCP) > 15
 
 
AND
 
 
• Transpulmonary Gradient (TPG) > 12
 
 
WHO Group III PH (n = 10)          Has WHO functional class II-IV symptoms          Had the diagnosis of PH confirmed by a cardiac catheterization with the following values:
 
 
○ Mean pulmonary artery pressure (mPAP) ≥ 25 mm Hg (at rest)
 
○ PCWP or left ventricular-end diastolic pressure ≤15 mm Hg (if diagnosed with PAH)
 

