### **2.13.2. Secondary Endpoints**

The secondary endpoints measure:

- Time to maximum PVR decrease;
- Repeated measures ANOVA (RM-ANOVA) for change in PVR calculated from the start of inhalation and at times 15, 30, 45 and 60 minutes post end of nebulization.
- Change in mean pulmonary artery pressure, transpulmonary gradient and cardiac output (CO)/cardiac index (CI),
- Change in systemic blood pressure,
- Change in SVR, RV systolic (dP/dtmax/IP, PWRmax/EDV, RV EF, TAPSE), RV diastolic function (dP/dtmin, Tau),
- Changes in pulmonary vascular impedance / Wave Intensity,
- Change in plasma nitrite concentrations, cGMP, and platelet mitochondrial activity in mixed venous blood at specified time-points,

Change in pulmonary artery occlusion (capillary) pullback nitrite and plasma cGMP at baseline compared with both nitrite doses.

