#### Safety Analysis

Adverse events (AEs) will be grouped by body system. AEs occurring pre-treatment, during active treatment and post-treatment will be summarized separately. The number and percentage of subject experiencing at least one AE of any type, AEs within each body system and AEs within each preferred term will be tabulated and listed. Separate summaries will be provided for all AEs, AEs by maximum severity, drug related AEs, severe adverse events (SAEs), and for AEs leading to withdrawal.

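### Aim 3 asks about blood pressure safety in patients on background PAH therapy, but the analysis plan defines no such population and no split by therapy

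*Combined protocol and SAP*

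**What the plan says.** Section 1.2 and the synopsis give Aim 3 as "To evaluate the safety of inhaled nitrite on systemic blood pressure in patients on background therapy for PAH". The safety hypothesis in section 1.2 has the same target: "We hypothesize that nitrite will be safe and well-tolerated in patients on background PAH therapy (PDE-5I and ETRA").

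Elsewhere the population varies:
- Section 1.1 reads as if every subject were treated: "in patients on background pulmonary hypertension therapy (ETRA, PDE5I, or prostacyclin analog").
- The synopsis objective makes therapy optional: "in patients that may be on background pulmonary hypertension therapy".
- The synopsis rationale, repeated in section 1.4, says "with or without background PH therapy".
- The synopsis entry criterion for Group I is conditional: "Stable PH for at least 3 months if on disease specific therapy". Section 3.2 has the same condition. Groups II and III, 30 of the 50 subjects, have no therapy criterion.

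The endpoint in section 2.13.2 is only "Change in systemic blood pressure", with no population attached. Section 2.15.2 plans a t-test of baseline against the highest tolerated dose and a repeated measures ANOVA across doses. Neither has a term or stratum for background therapy. The safety analysis tabulates "The number and percentage of subject experiencing at least one AE of any type" and then breaks events down by period, body system, preferred term, severity, relatedness, seriousness and withdrawal, but not by background therapy.

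**The concern.** Section 1.3.5 says that the interaction between inhaled nitrite and oral PAH drugs is unknown, singles out PDE-5 inhibitors, and gives this as the reason for keeping doses below the maximum tolerated dose. Section 5.1 repeats the PDE-5 inhibitor warning. Aim 3 is where the trial is meant to report on that risk.

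If enrolment mixes treated and untreated subjects and the analysis does not separate them, the reported mean change and event rates describe the mixture. A reassuring overall figure could then be read as evidence about treated patients when it rests partly, perhaps mostly, on untreated ones. The insight into nitrite with and without background therapy that the rationale offers also has no planned table behind it.

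**Working it through.** **Plan's own figure.** There is none for Aim 3. The only sample size, in section 2.15.1, is 14 subjects for a 10% fall in PVR from 911 with a spread of 102. Taking 102 as the SD of the paired change, the difference is 0.10 x 911 = 91.1, and an exact two-sided paired t-test at 0.05 with 80% power needs 12. Exactly 14 corresponds to an SD of change of about 108-112. That is close agreement, but it has no bearing on blood pressure.

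**Inputs.** Total N = 50 (20 + 20 + 10), from section 2.2.1. The treated share f, the extra fall in treated subjects and the SD of blood pressure change are not in the documents. Values of f and the extra fall below are assumptions, shown over a range.

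**Step 1: dilution of a mean.** The pooled mean is f x treated mean + (1 - f) x untreated mean, so the part of the extra fall that shows is f x extra fall.

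| Assumed share f | Extra fall 10 mm Hg | Extra fall 20 mm Hg |
|---|---|---|
| 20% (10 of 50) | 2 | 4 |
| 40% (20 of 50) | 4 | 8 |
| 60% (30 of 50) | 6 | 12 |
| 80% (40 of 50) | 8 | 16 |

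At f = 100%, the literal reading of section 1.1, there is no dilution.

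**Step 2: what zero events would show.** With no severe hypotension event in n subjects, the one-sided 95% upper bound on the rate is 1 - 0.05^(1/n).
- n = 50 pooled: 1 - 0.05^(1/50) = 5.8%
- n = 40 treated: 7.2%
- n = 30 treated: 9.5%
- n = 20 treated: 1 - 0.05^(1/20) = 13.9%
- n = 10 treated: 1 - 0.05^(1/10) = 25.9%

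This step needs no assumption about effect size, only the number treated. Quoting the pooled bound for treated patients would overstate what is known about them.

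**Step 3: what a split could detect.** By the normal approximation (two-sided 0.05, 80% power), the detectable treated-minus-untreated difference in SD units is (1.96 + 0.84) x sqrt(1/n1 + 1/n2).
- 10 against 40, or 40 against 10: 2.80 x 0.354 = 0.99 SD
- 20 against 30, or 30 against 20: 2.80 x 0.289 = 0.81 SD
- 25 against 25: 2.80 x 0.283 = 0.79 SD

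A split can therefore describe the treated subjects, but it cannot test for a modest interaction.

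**The case against.** **The plan never says it pools.** This is true. Sections 2.13.2 and 2.15.2 are silent on population, Aim 3 names its own, and section 2.15.1 sizes the primary outcome on about 20 Group I patients, so pooling over all 50 is not established. A reader might infer a stated decision to combine everyone; the text supports only an absence of restriction. That absence is still a defect. On either reading Aim 3 has no specified analysis, and a subgroup chosen after open-label data are in hand carries less weight.

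**The dilution may be small.** This also stands. A reader might assume that only a minority is treated, for instance because only Group I's criterion mentions therapy (20/50 = 40%), and conclude that most of an excess would be lost. The documents do not support that ceiling: Groups II and III are neither required to have therapy nor barred from it, and at an 80% share most of the excess would show.

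**Subjects are protected anyway.** Correct. Table 1 and the stopping rules in sections 2.6 and 5.5.2 apply to each subject's own fall from pre-dose pressure, and serious, unexpected, treatment-related events are summarised for the DSMB. It would be wrong to infer that a severe fall in one treated subject could go unnoticed through averaging. The weakness is in what Aim 3 can conclude.

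**The data would allow the split.** Yes. Concomitant medications are recorded (sections 2.12.5 and 2.12.8), so it cannot be said that the trial is unable to answer. The analysis is simply not planned.

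**Oral therapy is held on the study day.** This is the most serious limit. The synopsis and section 2.2.1 have subjects hold oral ETRA and PDE-5 inhibitors, so exposure at dosing is reduced by an amount the documents do not give, and no split can recover it. The hold does not name prostacyclin analogs, which the objectives include. This limits the remedy but does not remove the mismatch between aim and analysis.

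**Conclusion.** The point holds as a mismatch between a stated aim and its analysis. Aim 3 and the safety hypotheses concern treated patients, entry does not require treatment, and section 2.15.2 neither restricts nor splits by it. This should be corrected, because the protocol itself presents the interaction as an open safety question.

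The amount of dilution cannot be fixed. Over assumed shares of 20% to 80% and an assumed excess of 10-20 mm Hg, between 2 and 16 mm Hg would show in the pooled mean. The firmer consequence is precision: with zero events, the bound for 10 to 20 treated subjects is 25.9% to 13.9%, against 5.8% for all 50. The documents do not support the stronger conclusions that an interaction is certain to be masked, or that subjects are at added risk because of the analysis plan.

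**What to change.** In section 2.15.2:
- Define the Aim 3 population as subjects on background PAH therapy, and state how many are expected.
- Report the change in systolic and mean arterial pressure with 95% confidence intervals, and the number with hypotension meeting the Table 1 criteria with an interval for the proportion, for subjects on any background therapy and for those on none.
- Show any PDE-5 inhibitor use, alone or in combination, as a separate row. Drug classes overlap in patients on combinations, so they should not be presented as exclusive categories.
- Label the comparison descriptive. State that it is non-randomised and imprecise, that therapy may track WHO group, and that oral ETRA and PDE-5 inhibitors are held on the study day, so the result does not describe full concurrent exposure.

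Separately, reconcile the hold instruction with Aim 3, and reconcile section 1.1 with the synopsis objective, the synopsis rationale and section 1.4 on whether background therapy is required or optional.

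The cost is a few table rows and some text. Concomitant medications and blood pressure are already collected, so no added visits, procedures or subjects are needed. The price is wide intervals, which the report should show as they are.

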## 1.3 BACKGROUND

### 1.3.1. Pulmonary Arterial Hypertension

Pulmonary arterial hypertension (PAH) is a relatively rare and devastating illness characterized by high morbidity and mortality rates. The 1993 American College of Chest Physicians consensus statement reports that the incidence ranges from one to two cases per million. PAH shows a female bias with F:M ratio of 2.3:1. The median age at diagnosis is 36. In the NIH registry, the diagnosis of pulmonary hypertension required a mean pulmonary artery pressure greater than 25 mm Hg at rest or greater than 30 mm Hg with exercise. PAH may occur in either sporadic or familial forms. Six percent of subjects in the NIH registry had a first-order relative with PAH. Familial PPH is inherited as an autosomal dominant disorder with incomplete penetrance, and has been mapped to a locus designated PPH1 on chromosome 2q33 that produces loss of function mutations in *BMPR2*. Bone morphogenetic proteins, members of the transforming growth factor- $\beta$  (TGF- $\beta$ ) superfamily of signaling molecules, regulate cell differentiation and proliferation, apoptosis, morphogenesis and cell fate determination. Identified defects of this receptor are predicted to disrupt ligand binding, kinase activity, and heteromeric dimer formation – cellular processes that may ultimately be important in the maintenance of blood vessel integrity.

Familial and sporadic PAH appear to be phenotypically identical. The median survival for all subjects in the NIH registry was 2.8 years; the one, three, and five year survivals were 68%, 48%, and 34%, respectively. With the advent of epoprostenol therapy, the one, three, and five year survivals for PAH subjects have improved to 87%, 63%, and 54%, respectively. Despite these improvements in outcome, mortality remains unacceptably high. The lack of a routine screening test for PAH, and the fact that early symptoms are nonspecific ensures that subjects typically present with advanced disease.

Pulmonary hypertension is characterized by high pulmonary artery pressures and a high resistance to blood flow. The development of clinical PPA may be contingent on a genetic susceptibility (“hit” one) combined with an inciting injurious event(s) to the pulmonary artery EC (“hit” two) that renders it dysfunctional. The inciting event(s) probably cause a state of recurrent or chronic pulmonary vascular injury and repair, resulting in an excessive and adverse vascular remodeling process with associated alterations in gene expression. Adverse vascular remodeling and EC dysfunction results in excessive growth factor expression, decreased eNOS expression and NO production, vascular smooth muscle dysfunction, *in situ* thrombosis and a deficiency in endogenous prostacyclin synthesis

### 1.3.2. Investigational Drug

The active ingredient in AIR001 Inhalation Solution is sodium nitrite in a phosphate-buffered, pH adjusted solution for nebulization. Pre-clinical data suggest that under the hypoxic, acidemic conditions present in the pulmonary hypertensive lung, inhaled nitrite results in the sustained release of NO which will act as an acute pulmonary vasodilator. In addition, because decreased levels of NO have been shown to stimulate vascular remodeling, the increased NO resulting from nitrite inhalation is postulated to attenuate or reverse the remodeling process, resulting in sustained pulmonary hemodynamic improvement in subjects with PAH.

### **1.3.3. Inhaled NO for Pulmonary Hypertension**

Nitric oxide released from the endothelium as a gas or attached to transport molecules activates soluble guanylyl cyclase in smooth muscle after binding to its heme group, resulting in increased cyclic GMP. Cyclic GMP activates GMP-dependent kinases that decrease intracellular calcium concentration in smooth muscle, producing relaxation. Nitric oxide also inhibits synthesis of a potent constrictor peptide, endothelin-1, an action that may contribute to vasodilation. Inhaled NO may prove efficacious in patients with sickle cell disease and secondary pulmonary hypertension due to its ability to selectively dilate the pulmonary vasculature. Nitric oxide diffuses to ventilated alveoli and dilates the blood vessels subserving these gas exchange units but is then inactivated by hemoglobin, preventing systemic hypotension. This results in a selective reduction in pulmonary artery pressures.

Inhaled nitric oxide (NO) is a potent acute vasodilator and results in improved hemodynamics in the 15% of PAH subjects who demonstrate vasoreactivity. However, the usefulness of NO for chronic therapy is limited by the need for continuous inhalation. In subjects who demonstrate vasoreactivity during an acute challenge with inhaled NO or a prostanoid challenge, therapy with calcium channel blockers has been demonstrated to result in improved symptoms and survival. In subjects who do not demonstrate an acute vasodilator response, available therapies for PAH include prostanoids, ETRA, and PDE-5I. Inhaled NO is now one of the currently used drugs for vasodilator challenges in the cardiac catheterization laboratory and therefore will be used as a comparator for nitrite responses in the current study.

Inhaled NO will be delivered using FDA approved doses of 40 ppm for approximately 5-15 minutes as used routinely in the catheterization laboratory for evaluation of pulmonary vascular responses in patients with PAH. At doses up to 80 ppm (40 ppm will be used in this study) inhaled nitric oxide rarely produces adverse effects. Buildup of NO-O2 reaction products in tubing such as NO2, a molecule that can precipitate bronchospasm and pulmonary edema, can occur if the NO delivery system is not purged daily. The system will be purged prior to use, and inhaled levels of NO2 maintained well below 1 ppm. The INOvent NO delivery system that will be used in this study continuously monitors inhaled NO and NO2. NO will only be used as clinically indicated using standard methodologies to evaluate pulmonary arterial vasodilatory capacity.

### **1.3.4 Effects of nitrate and nitrite on mitochondria and metabolism.**

Mitochondria are critical for oxidizing fuels (i.e., glucose, fatty acids, amino acids) for cellular energy production. Accumulating evidence suggests that mitochondria dysfunction, characterized by decreased mitochondrial number, altered mitochondrial ROS generation or decreased substrate metabolism is associated with insulin resistance within skeletal muscle. A human *in vivo* study by Larsen et al recently reported that skeletal muscle mitochondria harvested after dietary nitrate supplementation displayed improved mitochondrial efficiency. These findings suggest that dietary nitrate enhances the efficiency of energy generation through direct effects on muscle mitochondria and may have implications in the metabolic syndrome where mitochondrial dysfunction may play a central role.

During ischemia nitrite is reduced to NO and N2O3 by different nitrite reductase enzyme

systems. Mitochondrial NO and S-nitrosothiols formed from nitrite dynamically and reversibly inhibit complex I during reperfusion, which limits ROS formation from complex I and III. This ultimately prevents the opening of the mitochondrial permeability transition pore and the release of cytochrome *c*. It has recently been shown that the site of nitrosation is on Cys 39 of the ND3 subunit of complex I. A number of enzymes are required to convert nitrite into NO during organ ischemia. For example, in the heart, deoxygenated myoglobin acts as a functional nitrite reductase. Nitrite-dependent NO formation is significantly decreased in myoglobin deficient hearts and nitrite administration reduces myocardial infarction with abrogated effects in the myoglobin knockout mice. These studies by the [name] and [name] laboratories have demonstrated that nitrite is a potent cytoprotective agent to mitochondria after ischemia and reoxygenation by inhibiting mitochondrial complex I activity, thereby blocking electron transfer and blocking the formation of superoxide during reperfusion. Further, nitrite has been shown to induce the expression of PGC1a as well as the mitochondrial biogenesis pathway in other cell types. These data suggest that nitrite inhibits mitochondrial respiration and attenuates mitochondrial ROS generation. Preliminary data from our research team suggest that nitrite specifically inhibits platelet mitochondrial basal respiration and enhances maximal respiratory capacity *in vivo*, effects which potentially decrease mitochondrial ROS generation and enhance substrate utilization in the platelet thereby attenuating platelet activation.

Measurement of platelet mitochondrial respiration and dysfunction from a standard blood draw. We have now developed new methodologies to measure mitochondrial function and respiration in isolated platelets. Considering emerging data on the role of nitrite and NO in regulating mitochondrial function, we plan to obtain fresh platelets to utilize with extracellular flux analysis (XF analysis (XF24, Seahorse Biosciences, Billerica, MA), a high throughput methodology to evaluate mitochondrial bioenergetics. We aim to measure platelet cell mitochondrial function before and after nitrite inhalation studies. Further, platelet mitochondrial bioenergetics will be measured along with thrombotic activation in patients with pulmonary hypertension.

